6.4.3 Permitted Concomitant Medications

At the discretion of the Investigator, the following concomitant medications may be used in accordance with the restrictions described for each treatment:

• All subjects will be instructed to use daily intranasal saline irrigation as background treatment starting from Screening through the study duration.

- Subjects who have been on a stable regimen of inhaled corticosteroids (not containing MF) or leukotriene receptor antagonists for asthma for a minimum of 3 months prior to the Screening visit should remain on the same dosage throughout the study. Inhaled corticosteroid use must be limited to a stable low- or medium-dose as defined by guidelines established by the 2020 Global Initiative for Asthma Management and Prevention.^[1]
- If acute sinus infection is suspected at any time during the study, treatment with antibiotics or macrolides (for a maximum of 14 days) will be allowed after a clinic visit and according to the Investigator's judgment.
- For severe acute nasal blockage lasting a minimum of 3 consecutive days: a course of oxymetazoline nasal decongestant sprays for a maximum of 3 consecutive days and a total maximum of 10 days during the treatment period. [NOTE: Oxymetazoline cannot be used within 24 hours before CT assessments.]
- Nonsedating oral antihistamine such as loratadine (10 mg per day) or equivalent for acute allergic symptoms.
- Perennial allergic rhinitis subjects who have been on a stable regimen of a nonsedating oral antihistamine for a minimum of 3 months prior to the Screening visit should remain on the same dosage throughout the study.

6.4.4 Rescue Concomitant Medications and Treatment

The following rescue medication is recommended for a worsening or uncontrolled severe CRS symptoms that last for a minimum of 3 days and result in the subject contacting the Investigator who determines an initiation of rescue treatment is necessary at any time during the study:

- A course of oral corticosteroids. Typical indications include persistent sinus infection after an initial course of antibiotics while starting another course of antibiotics, uncontrolled sinus inflammation, or a flare-up of asthma. The dose, duration of use, and rationale for the use of oral corticosteroid must be recorded.
- Sinonasal surgery as rescue treatment according to the Investigator's recommendation. The type and rationale for sinonasal surgery must be recorded.

6.5 Removal Procedure

Subjects will have the LYR-220 drug matrices removed bilaterally at the Week 24/EOT visit or earlier in an unscheduled early termination (ET) visit, if medically warranted according to the treating physician's discretion (eg, require sinonasal surgery as rescue treatment or use of any other MF medications). The removal procedure will be performed under endoscopic visualization after local anesthetic and decongestants applied to each nostril. Standard surgical tools are used to remove LYR-220. LYR-220 is made of polymers designed to gradually soften over time. Care should be taken to remove LYR-220 in 1 piece or in sections should any disintegration of LYR-220 occur.

To maintain blinding through the end of the study, subjects enrolled in the sham procedure group will undergo a sham removal procedure either at the scheduled Week 24 visit or earlier in an unscheduled early termination (ET) visit if the subject requests early study product removal.

6.6 Treatment Compliance

Administration and removal of LYR-220 and the sham procedure will be performed in a clinical setting by trained personnel who will be responsible for ensuring and recording compliance with all treatment procedures.

7. DRUG PRODUCT MATERIALS AND MANAGEMENT

[figure not shown]
7.1 Investigational Product

7.1.1 **Product Description**

The LYR-220 System is a combination product comprised of a single-use applicator, preloaded with an anti-inflammatory drug matrix. The LYR-220 drug matrix contains mometasone furoate (MF), an active ingredient in multiple FDA-approved products indicated for therapeutic and prophylactic management of seasonal and perennial allergic rhinitis (AR), nasal polyps, a phenotype of CS disease, as well as asthma. The LYR-220 drug matrix is designed to gradually soften over time and is made of bioabsorbable polymers that have been used as components of approved pharmaceutical drugs and/or medical devices.

[figure not shown]
LYR-220 has a tubular braid configuration with a uniform diamond pattern throughout. It is designed to be self-retaining against the mucosal tissues to allow effective drug transfer for up to 24 weeks. The matrix is comprised of a base structure and a drug formulation layer. The base structure is composed of poly(L-lactide-co-glycolide) and poly(L-lactide-co- ϵ -caprolactone) elastomer to provide a 3-dimensional structure and elasticity. The drug formulation layer consists of the active ingredient, MF, embedded in the inactive ingredients containing poly(L-lactide-co- ϵ -caprolactone) and poly(L-lactide) to control the release rate of MF. Two designs of LYR-220, LYR-220-32 drug matrix and LYR-220-16 drug matrix, manufactured with 32 and 16 woven fibers, respectively, will be assessed in this study (**Figure 2**). Both designs have the same nominal dimensions of 20 mm in diameter and 16 mm in length in the unconstrained state.

[figure not shown]
Figure 2: Images of the Two LYR-220 Drug Matrices

7.1.2 Dosage and Administration

Each LYR-220 drug matrix contains 7500 μ g MF. LYR-220 is intended to be administered bilaterally into the ethmoid cavity, in which ethmoid sinuses have been removed previously by a bilateral ethmoidectomy, by an otolaryngologist under endoscopic visualization using the provided single-use applicator (**Figure 3**). Once administered, each LYR-220 is designed to gradually deliver sustained doses of MF to the inflamed mucosal tissue over a 24-week resident time. Bilateral placement of LYR-220 (7500 μ g) is designed to deliver a total dose of 15,000 μ g MF over the 24 weeks, or an average daily dose of 89 μ g MF per person (or 45 μ g MF per nostril).

7.2 Drug Product Management

7.2.1 Packaging and Labeling

The investigational products (LYR-220 and sham) will be packaged and labeled, as required by regional legislation and industry guidelines. The LYR-220 System and sham products are individually packaged in a foil pouch, which is sterilized and placed within a shelf carton.

The Sponsor or designee will ship study products to the sites as needed. Specific instructions for ordering product will be provided to the sites.

7.2.2 Storage

It is recommended that the study product be stored at 15 °C to 25 °C (59 °F to 77 °F) and in the original packaging to protect from moisture and light. The labeled expiry dates are specified on the label. The location of drug product storage must be locked, and access must only be allowed to the study team or a designated person involved with the study team.

7.2.3 Product Traceability

Traceability of study products shall be achieved by assigning each product package a unique serial/kit number as described on the label.

7.2.4 Product Accountability

The Sponsor will supply sufficient quantities of LYR-220 and sham products to allow completion of the study. The Investigator or designee must maintain accurate records to document the disposition of all product received by the clinical site. Investigational sites will use a form to document product disposition which will be reviewed by the study monitor during routine monitoring visits. When enrollment in the Clinical Study is complete, any unused investigational product will be returned to Sponsor or discarded per Sponsor authorization along with a final Accountability Log. The Accountability Log must document the disposition of all investigational products including those that have been returned to the Sponsor.

7.2.5 Product Return

All products that are not administered into a subject must be returned to the Sponsor or designee or discarded per Sponsor authorization. Applicators successfully used for administration may be disposed on site after the study procedure is complete. For all investigational products that are associated with a malfunction, the products and all ancillary components (eg, applicator) remaining from the index procedure should be retained in case they need to be returned to the Sponsor. The Investigator will inform the Sponsor of any complaints or malfunctions during the study. The Sponsor will investigate all product complaints and malfunctions. Instructions for returning product will be provided to the sites by the Sponsor.

8. STUDY ASSESSMENTS

8.1 Study Schedule of Assessment

The schedule of study assessments for subjects is summarized in **Table 1** below and detailed in Sections 8.2, 8.3, and 8.4. All subjects in Part 1 and Part 2 will undergo these study assessments per the schedule.

Throughout the course of the study, all efforts will be made to remain alert to possible adverse events (AEs) or untoward findings. Any AEs observed by the Investigator or reported by the subjects, whether or not attributed to the investigational procedure or product, will be monitored and evaluated throughout the study. If AEs occur, the first concern will be the safety and welfare of the subject. Appropriate medical intervention will be undertaken per the treating physician's discretion.

Vital signs and a limited physical exam, focusing on physical appearance of head, eyes, ears, nose, and throat (HEENT) will be performed at Screening visit. Samples for hematology and chemistry will be collected at Screening and Week 25 visits.

Nasal cavities will be assessed by endoscopy at Screening, Day 1 before the LYR-220 insertion procedure, and at Weeks 4, 12, 24/EOT (before LYR-220 removal), and Week 25 visits. Local safety evaluation of the ethmoid cavity will be performed at these visits to document presence of epistaxis, mucosal injury, and any other local adverse effects. On Day 1 (before LYR-220 insertion) and at Week 25 visits, nasal swabs will be collected in ethmoid cavities to evaluate the impact of LYR-220 on nasal inflammatory marker level by protein and mRNA assays.

Ophthalmologic assessments will include IOP and slit-lamp examination during Screening and at Week 25 visit. IOP assessment will also be performed at Week 4 and 12 visits.

For female subjects of childbearing potential, a serum pregnancy test will be performed at the Screening visit and a urine pregnancy test will be performed on Day 1 prior to treatment to confirm eligibility for participating in the study. Additionally, a urine pregnancy test will be performed at Weeks 4, 12, and 24/EOT or ET visits in these female subjects.

Plasma samples for PK will be collected from all subjects at Day 1 pre-procedure, 1 hour (± 10 minutes) post procedure on Day 1, Day 2 or 3, Day 5 or 8, and Weeks 4, 12, 16 or 20, 24/EOT, and Week 25 visits.

Enrolled subjects will be asked to complete a daily ePRO questionnaire to assess the severity of the 4 CS of CRS (nasal blockage/obstruction/congestion, facial pain/pressure, anterior/posterior nasal discharge, and loss of smell). In addition, the ePRO will capture use of daily saline irrigation by the subjects. Subjects will also complete 2 validated CRS-specific quality of life questionnaires, the SNOT-22 and CRS-PRO, at Screening, on Day 1 before treatment, and at Weeks 2, 4, 6, 8, 12, 16, and 20, at Week 24 before matrix removal, and at Week 28/EOS. CRS-PRO will also be assessed at Day 8 and Week 3. The PGIS will be administered on Day 1

(pretreatment) and at Weeks 8, 16, and 24/EOT. The PGIC will be assessed at Week 24/EOT. At Week 28/EOS visit, an end-of-study questionnaire will be administered.

Ethmoid cavity opacification will be assessed by CT scans obtained during Screening (or using a historical scan taken within 3 months of Screening) and at Week 25 visit, unless medically contraindicated. Subjects will be instructed to stop use of saline rinse approximately 24 hours prior to the scheduled sinus CT. Daily saline irrigation should then continue following the sinus CT. If a subject is experiencing or recovering from a cold, acute exacerbation of nasal allergy, or upper respiratory tract infection at Week 25 visit, the CT assessment should be performed 4 weeks after resolution of the adverse event. If a subject early terminates from the study or requires SCS or sinonasal surgery as rescue treatment during the study, every attempt should be made to perform the follow-up CT before subject receives the rescue treatment.

LYRA THERAPEUTICS, INC. STUDY LYR-220-2021-001

VERSION 4.0 (30 AUG2022)

Enrolled
jects
Sub
s for
Assessment
$\mathbf{0f}$
hedule
Sc
Ξ
Table

		2															
		_						Treat	Treatment Stage	age						Post-	4
Evaluation	ing & Run-In	dure Day														Treatment Stage	ient je
Visits #	1	2	3	~	4		⊢	⊢	5	⊢	F	9	7/7	F	œ	6	10/T p
Study Day/Week	DAY - DAY - 28 (Day - 28 to Day 0)	DAY 1 (Day 1)	DAY 2 (Day 2)	DAY 3 (Day 3)	DAY 5 (Day 5)	DAY 8 (Day 8)	WK 2 (Day 15±1)	WK 3 (Day 22±2)	WK 4 (Day 29±3)	WK 6 (Day 43±3)	WK 8 (Day 57±3) ª	WK 12 (Day 85±3)	WK 16 (Day 113±3) ª	WK 20 (Day 141±3) ª	WK 24/EO T/ET (Day 169±7)	WK 25 (5-9 days after T)	WK 28 (EOS) (25-31 days after EOT)
Informed Consent	×c																
Demographics	×																
Medical History	Х																
Vital Signs	Х																
Limited Physical Exam ^I	Х																
Pregnancy Test ^f	Хe	X d,e							Хe			Хe			Хe		
Hematology/Chemistry ^f	Х															×	
Sinus CT	Х															X m, n	
PK		X d, o	X	g	Х	g			×			Х	Х	g	ЪХ	×	
Nasal Endoscopy	Х	Хi							×			Хi			X d, i	хi	
Ophthalmology (IOP and slit-lamp)	Х								٩X			ЧX				ж	
Eligibility Assessment	Х	Хd															
Nasal secretion & mucosal RNA (culture & cytology swabs)		γ														×	
Run-in	ЧX																
Randomization (Part 2 study only)		рX															
Insertion Procedure		\times															
Removal Procedure															×		
Daily 4CS ePRO j									×								
SNOT-22 Questionnaire j	Хr	X d, r					Хr		Хr	Хr	Хr	Хr	Хr	Xr	X d, r		Хr
CRS-PRO Questionnaire J	Xs	X d, s				Xs	Xs	Xs	Xs	Xs	Xs	Xs	Xs	Xs	X d, s		Xs
PGIS		X d,q									٩X		٨٩		٩X		

PROPRIETARY AND CONFIDENTIAL

STUDY LYR-220-2021-001 LYRA THERAPEUTICS, INC.

VERSION 4.0 (30 AUG2022)

Evaluation	Screen Proce ing & dure Run-In Day	Proce dure Day						Trea	Treatment Stage	age						Post- Treatment Stage	st- nent ge
Visits #	1	2	3			4	T	Т	5	Г	Т	9	7/7	Т	8	6	10/T P
Study Day/Week	DAY - 28 (Day - 28 to Day 0)	DAY - 28 (Day - DAY 1 28 to (Day Day 0) 1)	DAY 2 (Day 2)	DAY 3 (Day 3)	DAY 5 (Day 5)	DAY 3 DAY 5 DAY 8 (Day 3) (Day 5) (Day 8)	WK 2 (Day 15±1)	WK 3 (Day 22±2)	WK 4 (Day 29±3)	WK 6 (Day 43±3)	WK 8 (Day 57±3)ª	WK 12 (Day 85±3)	WK 16 (Day 113±3) ª	WK 8 WK 16 WK 20 24/E0 WK 20 24/E0 Uay WK 12 (Day (Day (Day (Day (Day (Day T/ET 57±3) ^a (Day 113±3) 141±3) (Day 185±3) a	WK 24/EO T/ET (Day 169±7)	NK 25 (5-9 days after T)	WK 28 (EOS) (25-31 days after EOT)
PGIC															۶d		
End-of-Study Questionnaire																	×
Concomitant Medications/Procedures									Х								
Adverse Events ^k									×								
Λ the avioration of Λ of Λ and Λ is a state of Λ and Λ is a state of the state of Λ and Λ is a state of Λ and Λ and Λ and Λ is a state of Λ and	ntome of	CDC. aD	DO = ala	otronio r	votiont re	anorted of	intromac.	T - Tala	shone fo	11011 110.	EOT - 2	and of the	otmont.	ET - and	tornoi u	ation.	

EOS = end-of-study; IOP = intraocular pressure; PGIC = Patient Global Impression of Change; PGIS = Patient Global Impression of Severity; PK = pharmacokinetic testing; RNA Abbreviations: 4CS = 4 cardinal symptoms of CKS; ePRO = electronic patient-reported outcomes; T = Telephone follow-up; EOT = end of-treatment; ET = early termination; = ribonucleic acid; SNOT = 22-item Sino-Nasal Outcome Test; WK=week.

Phone follow-up to collect any potential AEs and use of concomitant medications/procedures. a:

IOP assessment only. ġ.

- Informed consent to be obtained before any study-related assessments occur. ö
- Occurs before the LYR-220/sham insertion on Day 1 or removal procedures at Week 24. ų:
- Complete a serum pregnancy test at initial Screening visit and a urine pregnancy test in clinic at all subsequent visits during the treatment stage for female subjects of childbearing potential. ö
 - investigators must document their review of each laboratory report.
- Subjects return to clinic for PK assessment at only 1 of 2 timepoints at Visits 3 and 4. Subjects return to clinic for Visit 7 PK assessment either at Week 16 or Week 20; a telephone follow-up will be performed the week the subject is not returning for a PK draw. ii ii
 - Subjects will start daily saline irrigation during run-in period. н. Б
- Nasal safety assessments of ethmoid cavity including epistaxis, mucosal injury, and any other adverse findings will be performed on Day 1 (before LYR-220 insertion) and at Week 4, 12, 24/EOT, and 25 visits.
 - Daily (between 06:00.00AM and 11:59:59AM) cardinal CRS symptoms, to be recorded by the subject on ePRO questionnaire beginning at least 14 days preceding or on Day 1 visit (prior to randomization). ·--
 - All adverse events shall be reported after subject signs informed consent.
 - A physical examination of the head, eyes, ears, nose, and throat (HEENT). ы ні ні кі
 - To be performed within 5-9 days after removal procedure.
- If a subject is experiencing or recovering from a cold, acute exacerbation of nasal allergy, or upper respiratory tract infection at the Week 25/EOS visit, the CT assessment should be performed 4 weeks after resolution of the adverse event.
 - A blood sample for PK assessment should be collected 1 hour (±10 minutes) after bilateral LYR-220 insertion.
 - Week 28/EOS follow-up may be performed either as a telephone follow-up or an in-clinic visit (if subjects need to return a study supplied ePRO device).
 - It is recommended that the PGIS be completed after the 4CS questionnaire. The PGIS should be completed before the PGIC.
 - SNOT-22 to be recorded by the subject based on a recall period of 2 weeks (14 days) prior to visit.
 - CRS-PRO to be recorded by the subject based on a recall period of 7 days prior to the visit.

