Data collected in this study will be presented using listings, as well as summary tables and figures. Continuous data will be summarized by treatment group using the following descriptive statistics: the number of observations (n), mean, standard deviation (SD), median, minimum, and maximum. Categorical data will be summarized by treatment group as number and percentage of subjects in each category. Individual subject's data will be presented in listings.

Subject Disposition and Demographic Characteristics:

Subject disposition will be summarized for all consented subjects. Analysis set assignment will be summarized for all enrolled subjects by treatment group. Demographics and other baseline characteristics and study drug exposure will be summarized for the Efficacy analysis set.

PK Analyses:

The PK analyses will be performed based on subjects with available plasma MF concentration data post Day 1 LYR-220 administration procedure. A summary table will be used to present descriptive statistics (number, mean, SD, coefficient of variation, median, minimum, and maximum) of these PK parameters by treatment group. If plasma MF levels are detectable, PK parameters of MF will be estimated using a standard noncompartmental PK approach based on individual plasma concentration-time data. Maximum concentration (C_{max}) and time to reach maximum concentration (T_{max}) will be taken directly from the observed data. Actual PK sampling times will be used in the derivation of PK parameters. There will be no imputation of missing data.

Safety Analyses:

Safety will be assessed through AEs and changes in laboratory tests, vital signs, nasal endoscopy assessment, IOP and slit-lamp examination using the safety analysis set. AEs will be coded by using the Medical Dictionary for Regulatory Activities (MedDRA) dictionary.

The number and percentage of subjects with incidence of the safety endpoints will be presented by treatment group, where subjects will be classified according to the treatment received. There will be no formal statistical tests comparing treatments on safety endpoints. There will be no imputation of missing data.

Efficacy Analyses:

All efficacy analyses will be carried out after the last subject completes the Week 28 visit or withdraws prematurely prior to Week 28.

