4.1.1 Screening and Run-in Stage

After providing written informed consent, subjects who are qualified to participate in this study will have an initial Screening visit. Immediately following the initial Screening visit, subjects will undergo a 2–4-week run-in period. The run-in period is more than 5 elimination half-lives of MF (5.8 hours)^[35] as recommended by FDA guidelines.^[36] During this run-in period, except for a background therapy of daily saline irrigation, subjects will receive no other active treatment for CRS or any prohibited or rescue medications specified in the study protocol (Sections 6.4.2 and 6.4.4, respectively).

If a subject fails the initial screening, they are permitted to be rescreened under a new subject ID. If a patient is eligible for rescreening, the sinus CT and IOP/slit lamp assessments do not need to be repeated if the assessments were done within 4 months of rescreening and there were no significant changes in the subject's medical history according to the Investigator's judgement.

Subjects who fail screening due to administrative reasons (eg, visit window) or another screening assessment may be allowed to repeat certain screening assessment(s) and re-establish eligibility. Documentation of the decision will be filed in the subject's file.

Subjects will be provided with saline and instructions for daily intranasal saline irrigation starting from the Screening visit throughout the study. Subjects will be instructed to stop use of saline rinse approximately 24 hours prior to the scheduled sinus CT. Daily saline irrigation should then continue following the sinus CT. Daily saline irrigation procedures should adhere to the Investigator's prescribing information and local standards, as applicable.

Beginning at least 14 days prior to LYR-220 insertion procedure on Treatment Day (Day 1), subjects will record daily cardinal symptoms (CS) of CRS on the electronic patient-reported outcomes (ePRO) questionnaire. At Screening, the SNOT-22 and CRS-PRO will also be collected.

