If **spontaneous dislodgement of LYR-220** occurs before the scheduled Week 24/EOT visit, subjects are required to call the study clinic immediately to report the event. If a subject experiences dislodgement of 1 of the bilateral matrices, the subject will continue in the treatment phase unless an early treatment discontinuation is recommended by the treating physician or subject requests matrix removal from the remaining side of the nose. If matrices spontaneously dislodge from both sides of the nose, the subject will complete an unscheduled **early-termination (ET)** visit within 7 days of the second matrix dislodgement, and complete the assessments scheduled for the Week 24/EOT visit. Spontaneously dislodged LYR-220 should be retained, if available, and returned to the clinic at subject's next visit.

If medically warranted according to the treating physician's discretion (for example, needing sinonasal surgery as rescue treatment), early matrix removal may be performed at an unscheduled ET visit.

Any subject who undergoes an ET visit is required to complete the assessments scheduled for the Week 24/EOT visit and should stay in the study and complete the assessments scheduled for the Week 25 visit within 5-9 days after the ET visit.

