8.3.2 Vital Signs

Vital signs will be measured at the screening visit as specified in the Schedule of Assessments (Section 8.1). Vital sign measurements will include blood pressure (systolic and diastolic, mm Hg), and pulse rate (beats per minute), aural/oral temperature (°C or °F), and respiration rate (breaths per minute). All measurements will be obtained after the subject has been seated for at least 5 minutes.

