8.3.8 Pharmacokinetic Analysis

Blood samples for assessment of plasma PK will be collected from all subjects on 9 occasions as specified in the Schedule of Assessments (Section 8.1):

- Day 1 pre-procedure
- 1 hour (±10 minutes) post procedure on Day 1
- Day 2 or 3
- Day 5 or 8
- Week 4
- Week 12
- Week 16 or 20
- Week 24/EOT, and
- Week 25

At the Day 1 visit, the blood samples for plasma PK analysis will be collected before the LYR-220 administration procedure and 1 hour (± 10 minutes) after the procedure. At the Week 24/EOT visit, the blood sample will be collected before the LYR-220 removal procedure. Blood samples may be collected at any time of the day during all the other scheduled study visits. The concentration of MF in plasma will be measured at a central core lab.

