8.4.2 Ethmoid Cavity Opacification Imaging

Ethmoid cavity opacification will be assessed by CT at the time points specified in the Schedule of Assessments (Section 8.1), unless medically contraindicated. The Screening CT should be performed anytime between the Screening and Day 1 visits. Alternatively, a historical CT scan can be used if done within 3 months preceding the Screening visit. The follow-up CT will be conducted within 5-9 days after the LYR-220 removal procedure at Week 25 visit. If a subject is experiencing or recovering from a cold, acute exacerbation of nasal allergy, or upper respiratory tract infection at the Week 25 visit, the CT assessment should be performed 4 weeks after resolution of the adverse event. If a subject early terminates from the study or requires SCS or sinonasal surgery as rescue treatment during the study, every attempt should be made to perform the follow-up CT before subject receives the rescue treatment. The percent opacification of ethmoid cavity will be evaluated by an imaging core lab.

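### No laboratory tests or vital signs are scheduled during the 24-week treatment stage; the only post-baseline laboratory sample, 5-9 days after removal, can show only changes that persist

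*Protocol*

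**What the plan says.** Protocol 8.1 states: "Samples for hematology and chemistry will be collected at Screening and Week 25 visits". Sections 8.3.3.1 and 8.3.3.2 and SAP 3.6.2 give the same two visits.

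Exposure ends at removal: "Subjects will have the LYR-220 drug matrices removed bilaterally at the Week 24/EOT visit or earlier in an unscheduled early termination (ET) visit" (Protocol 6.5). The Week 25 visit follows 5-9 days later. Protocol 8.4.2 gives that interval for the CT at the same visit: "The follow-up CT will be conducted within 5-9 days after the LYR-220 removal procedure at Week 25 visit". Protocol 4.1.2 asks subjects who terminate early to "complete the assessments scheduled for the Week 25 visit within 5-9 days after the ET visit".

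For vital signs, Protocol 8.3.2 says "Vital signs will be measured at the screening visit as specified in the Schedule of Assessments". SAP 3.6.4 repeats this and plans a summary of values only.

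Other parts of the plan rely on these data:

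- The synopsis says "Safety will be assessed through AEs and changes in laboratory tests, vital signs, nasal endoscopy assessment, IOP and slit-lamp examination".
- Clinically significant abnormal laboratory values through Week 25 are a secondary safety endpoint (Protocol 3, SAP 2.3.2).
- Protocol 9.6 plans laboratory change from baseline. SAP 3.6.2 plans values only.
- Protocol 8.3.12 names laboratory results and vital signs among the data for safety monitoring.
- Protocol 4.3 counts a severe laboratory abnormality among the reasons for stopping study treatment.

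**The concern.** Safety, tolerability and pharmacokinetics are the stated purpose of the trial (Protocol 4.2 and 9.1), and Protocol 11 says that LYR-220 has not been used in humans before. Yet the systemic laboratory measures are taken before the drug goes in and again after it has come out. A steroid effect on glucose, electrolytes or white cells that appeared during treatment and reversed within days of removal would leave no trace in the laboratory tables. A clean laboratory endpoint would then be hard to interpret: a reader could not tell whether there was no effect or an effect that had already resolved.

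For vital signs there is no post-baseline value at all. The safety monitoring and the discontinuation reason also refer to data that no scheduled visit supplies before removal. Those passages need to be reconciled with the schedule.

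**Working it through.** **Inputs.** Half-life 5.8 h and the five-half-life criterion: Protocol 4.1.1, "The run-in period is more than 5 elimination half-lives of MF (5.8 hours". Run-in 2-4 weeks: the same section. Lag from removal or ET to Week 25, 5-9 days: Protocol 4.1.2, 8.4.2 and Table 1. ET visit within 7 days of the second dislodgement: Protocol 4.1.2. Laboratory window: SAP Table 2a.

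**1. The protocol's own statement.** 5 x 5.8 h = 29 h, or 1.21 days. The run-in is 14 x 24 = 336 h to 28 x 24 = 672 h. 336/5.8 = 57.9 and 672/5.8 = 115.9 half-lives. The claim of more than five half-lives reproduces.

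**2. The laboratory sample.** 5 x 24 = 120 h and 9 x 24 = 216 h. 120/29 = 4.1 and 216/29 = 7.4, so the sample comes at about 4 to 7 times the washout period. In half-lives this is 120/5.8 = 20.7 to 216/5.8 = 37.2. If 5.8 h were read as the total for five half-lives, the washout would be shorter and the comparison would go the same way.

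**3. Sensitivity to the half-life.** For the sample to fall within five half-lives, the effective half-life after removal would have to be at least 120/5 = 24 h (day 5) or 216/5 = 43.2 h (day 9).

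**4. Bilateral dislodgement.** Up to 7 days to the ET visit plus up to 9 more gives a sample as late as 16 days after exposure ends.

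**5. Counts over 24 x 7 = 168 days of treatment.** Scheduled laboratory panels: 0. Scheduled vital signs after Screening: 0. PK blood is planned on nine occasions. Leaving out the pre-procedure and Week 25 draws, seven fall between insertion and removal. One of them is at the needed time: "At the Week 24/EOT visit, the blood sample will be collected before the LYR-220 removal procedure".

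**6. The exception.** Protocol 8.3.6 asks sites to try to complete the Week 25 assessments before systemic corticosteroids start, while study treatment continues. Such a sample could be taken with the matrices in place. SAP Table 2a accepts laboratory results only from Aenday 0 to Aenday 31. Taking Aenday 0 as the day of removal, a sample drawn earlier fits no window, and under SAP 3.1.2 it is listed but not tabulated.

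**7. Why a Week 24 sample needs its own window.** A removal-day sample is Aenday 0, already inside the Week 25 window with target Aenday 7. It lies 7 days from target. A sample at Aenday 5-9 lies at most 2 days away. Under the closest-to-target rule in SAP 3.1.2 the removal-day result would be discarded.

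**The case against.** Much of the opposing case is sound.

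- A reader might infer that the laboratory data cannot show any drug effect. That goes too far. A Screening-to-Week 25 change can be computed, and an abnormality that arose on drug and persisted would be seen.
- A reader might infer from the half-life that all systemic drug is gone when the sample is drawn. The documents do not say so. The 5.8 h figure justifies the run-in. It is not stated to bound elimination after a depot is removed, or recovery of laboratory values. Protocol 2.2 allows that remnants may be left behind, and PK is still sampled at Week 25.
- A reader might take the comparison with an inhaled asthma regimen in Protocol 11 as an admitted systemic risk. The protocol offers it as reassurance, and it reports no significant fall in morning cortisol at Weeks 4, 12 and 24 in the LYR-210 Phase II study. That is fair background, though LYR-220 is a different matrix at a different site, and its panel has no cortisol.
- Treatment is not unobserved. PK, IOP at Weeks 4 and 12, AE review at each office visit and medical monitoring all run during exposure. A symptomatic effect could be reported; a silent biochemical one would not reliably be.
- The laboratory endpoint runs through Week 25 and is sampled at Week 25, so there is no contradiction in it. An earlier sample is a better design choice, not a correction of an error.
- Vital signs are in no endpoint, and Protocol 9.6 omits them. The inconsistency lies in the synopsis and in 8.3.12.

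Timing also counts. The SAP is dated 24 August 2023, and its primary lock follows the last Week 24 visit, in support of a September 2023 presentation. A change made at that stage would reach few subjects, if any.

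**Conclusion.** The point stands in limited form. There are no scheduled laboratory or vital-sign measurements in 168 days of treatment. The one post-baseline laboratory sample comes 120-216 h after removal or the ET visit, against a 29 h washout figure, and is informative only about changes that last that long. How much is missed depends on how quickly any effect reverses, which the documents do not give.

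The vital-signs part needs no such assumption: with one pre-treatment reading, no change exists to analyse. Even if the word for change in the synopsis is read as covering laboratory tests only, a Screening value says nothing about treatment.

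The conclusion assumes that Aenday 0 is the day of removal and that no extra tests are ordered outside the schedule. The pre-rescue exception covers few situations and mostly does not reach the summary tables.

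**What to change.** - Draw the haematology and chemistry panel at Week 24/EOT, or at ET, before removal and with the PK blood already scheduled. It can replace the Week 25 sample or be added to it. Adding it keeps the view of persistence; replacing it means rewording the endpoint's time frame. After bilateral dislodgement the ET sample is still off drug, but earlier than Week 25.
- In SAP Table 2a, separate the laboratory rows from the slit-lamp row. Add a laboratory Week 24 row that includes Aenday 0, and start the laboratory Week 25 window at Aenday 1, as Table 2b does for endoscopy. The windows then do not overlap.
- Record vital signs at the same visit, or remove them from the synopsis list of safety measures and reconcile Protocol 8.3.12.
- Reconcile SAP 3.6.2 with the change-from-baseline summary in Protocol 9.6.
- If sampling can no longer be changed, label the laboratory results as post-treatment in the tables and the study report.

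Cost: no extra visit or venepuncture; at most one more central-laboratory panel per subject (about 50); a few minutes for vital signs; and a protocol amendment handled under Protocol 10.5. The labelling option costs only wording.
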